Evolocumab in Patients With Acute MI NCT04082442 7/14/2021 Date: 07/14/2021

Principal Investigator: [name]

Application Number: IRB00206305

JHM IRB - eForm A - Protocol

• Use the section headings to write the JHM IRB eForm A, inserting the appropriate material in each. If a section is not applicable, leave heading in and insert N/A.

• When submitting JHM IRB eForm A (new or revised), enter the date submitted to the field at the top of JHM IRB eForm A.

1. Abstract

a. Provide no more than a one page research abstract briefly stating the problem, the research hypothesis, and the importance of the research.

Despite aggressive early intervention and current secondary prevention strategies, hundreds of thousands of patients who survive hospitalization for acute coronary syndrome (ACS) experience subsequent unfavorable outcomes, including recurrent ischemic events and unfavorable cardiac remodeling associated with progressive left ventricular dysfunction and congestive heart failure. Vascular and myocardial inflammation are significantly increased in ACS patients, are closely correlated to LDL-C levels, and are associated with these adverse consequences in the post-ACS patient population. Inflammation may also play a role in increased platelet aggregation one of the responsible mechanisms for the index and for recurrent coronary thrombotic events. Serum proprotein convertase subtilisin/kerin type 9 (PCSK9) levels are also increased in ACS, may raise LDL-C, and our pre-clinical studies indicate that PCSK9 is also a potent inducer of vascular inflammation. The addition of the PCSK9 antibody evolocumab, currently approved to lower LDL-C in certain patient populations, to current medical therapies may be of particular benefit in an important subset of ACS patients, those with ST-elevation and non-ST-elevation myocardial inflammation-associated myocardial cell loss and resultant dysfunction.

Hypothesis: In a placebo-controlled, randomized double blind trial, the addition of the PCSK9 antibody evolocumab to standard care in ST-elevation (STEMI) and non-ST elevation (NSTEMI) patients (1) decreases LDL-C during hospitalization and at 25-30 days, (2) decreases vascular/plaque and myocardial inflammation as assessed by PET scanning at 25-30 days, and improves (3) serum markers of endothelial function and of platelet function at hospital discharge, and at 25-30 days (4) echocardiographic at 30 days and, in a subset of patients (5) magnetic resonance imaging (MRI) assessment of left ventricular function at six months.

This is the first PCSK9 inhibitor trial which examines these outcomes in the NSTEMI and STEMI patient population. It will provide valuable data on the extent and time course of LDL-C reduction as well as the impact of PCSK9 inhibition and, we believe, of changes in inflammation on serum

pro-inflammatory markers and on imaging assessment of vascular and myocardial inflammation, all of which may significantly impact important clinical outcomes in this high risk patient cohort.[1]

Observation Study:

To further assess the trajectory of Lp(a) and other inflammatory mediators and markers in patients with acute myocardial infarction we are requesting permission to obtain samples from an additional 100 patients not enrolled in the current protocol, and not undergoing any research procedures other than venipuncture. They will be obtained from the time of early hospital evaluation, during hospitalization, and at 30 days. The first sample may that obtained clinically and sent to the laboratory during the early hospital evaluation, but not used by the laboratory (sometimes termed "remnant sample").

Rationale for the observation study:

The motivation for the study is two-fold. First, to more clearly define the trajectory of Lp(a) and other inflammatory serum and plasma markers/mediators in ACS patients and more specifically to obtain measures at the time of first presentation (e.g. in the Emergency Department) using any "remnant" samples obtained at that time. Second, to perform detailed proteomics on the samples using the sophisticated technology at Proteomics Bioanalytics. The company has an outstanding scientific publication record, and this is an opportunity for us to establish a relationship with them. The data will allow us to examine the importance of proteomic measures of potential inflammatory markers and mediators, which is a prime focus of my basic studies.

Although, as previously noted, Lp(a) is recognized as a risk factor for ACS patients, there has not until very recently, been an intervention specifically directed to that risk factor. Amgen (and Novartis) developed an intervention which works at the RNA-to-protein step in Lp(a) synthesis. Amgen is preparing a large phase 3 trial and may incorporate our data in a determination as to whether to include an "ACS arm" in their study.

2. Objectives (include all primary and secondary objectives): To conduct a placebo-controlled randomized, double blind study of the effect of the addition of evolocumab to standard care in NSTEMI and STEMI patients

2.1 Primary (for the intervention study group)

The primary objectives are the difference, in the evolocumab and placebo groups, in the mean % change in LDL-C from pre-randomization to 25-30 days.

Primary (for the observation study group)

The time course of inflammatory markers and mediators in those with acute myocardial infarction.

2.2 Secondary (for the intervention study group)

The secondary objectives are to compare in the evolocumab and placebo groups:

a. Serial serum markers of inflammation, platelet and endothelial cell function, lipids, and myocardial injury, and left ventricular function which will be collected at pre-randomization, during hospitalization, at hospital discharge and at 25-30 days, 6 months and 12 months follow up. In those who are discharged before day 3, and those who are unwilling or unable to return to the hospital, additional samples may be obtained in the out of hospital setting.

The time points of comparison are pre-randomization, during hospitalization, at hospital discharge, and any obtained in the outpatient setting including the 30 days, 6 months, and 12 months samples.

- i. PCSK-9
- ii. Soluble LOX-1
- iii. IL-6, IL-10, IL-12
- iv. hsCRP
- v. platelet function
- vi. LDL-Cholesterol
- vii. HDL-Cholesterol
- viii. Triglycerides
- ix. Total Cholesterol
- x. Apolipoprotein B
- xi. Lipoprotein (a)
- xii. Troponin
- xiii. Pro-BNP
- xiv. HbA1c
- xv. Insulin
- b. The change between hospitalization and thirty day of:
 - i. PET-FDG assessed myocardial inflammation and vascular inflammation in the most diseased segment of aorta or carotid artery. For this outcome, separate analyses will also be performed in those who did and did not undergo the initial PET scan within 48 hours of study drug administration.
 - ii. Echo assessed regional wall motion in the infarct territory
 - iii. Echo assessed global LV function
 - iv. Echo assessed LV systolic and diastolic volumes

The times of collection will be at early hospitalization and 30 days. The time point of comparison will be at 30 days

c. At thirty days:

- i. Comparison of PET-FDG assessment of myocardial inflammation and vascular inflammation in the evolocumab versus placebo group as described in 2.2. b i
- ii. Echo assessed as described in 2.2. b ii-iv
- iii. Angina class
- iv. New York Heart Association functional class
- v. Serum markers as described in 2.2. a

d. At six months

- i. Angina class
- ii. New York Heart Association functional class
- iii. Echo assessment as described in 2.2. b ii-iv

In a subset of participants: The change between early infarction period and six months assessments of Cardiac MRI-assessed adverse remodeling, e.g. LV function and volumes, infarct size and scar quantification

e. At 12 months

Serum markers as described in 2.2 a

Secondary (for the observation study group): The change in inflammatory markers and mediators between early hospitalization, during hospitalization, and at 30 days.

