This is a phase 2, double-blind, randomized, placebo controlled clinical trial of 420 mg evolocumab administered subcutaneously using an autoinjector/pen in NSTEMI and STEMI patients during early hospitalization at the Johns Hopkins Hospital and the Johns Hopkins Bayview Medical Center. The placebo and evolocumab will be given exactly the same way with the same Amgen provided device. All participants will receive standard care for NSTEMI and STEMI, including, as appropriate, high dose statin, aspirin, beta blocker, an angiotensin converting enzyme inhibitor or angiotensin receptor blocker, as well as angiography and reperfusion. High dose statin therapy consists of atorvastatin 40mg or 80mg or rosuvastatin 20mg or 40mg per the most recent ACC/AHA guidelines. [41] After signing informed consent, subjects will be randomized to receive one dose of evolocumab or matching placebo subcutaneously. Research blood samples for lipid profile, endothelial function, and inflammatory markers, and PET imaging assessment of myocardial and vascular inflammation as well as any clinically indicated echocardiographic studies for left ventricular function will also be obtained. Additionally, in a subset of patients we will obtain cardiac MRI studies. An independent Data and Safety Monitoring Committee will review all potential side effects and clinical outcomes during the six months of follow-up.

FDG/PET scans are not performed at Hopkins Bayview. If participants enrolled at that site are transferred to Hopkins Hospital for clinical care, and the scan can be performed during that hospitalization, it will be done so. For other patients, i.e. those discharged home from Bayview, or Hopkins patients who could not undergo the scan during their admission because of scheduling issues, the first scan will be performed on an outpatient basis. In those instances a car service will be arranged to transfer the participants to and from JHH and they will have three outpatient visits, for the initial and the follow-up 30 day scans, and for the six-month visit.

After hospital discharge, we will send a letter to the participant's physician(s) to inform them that the participant was enrolled in the study and that lipid values during the 4-5-week period after study drug administration may reflect the impact of evolovumab if the participant is randomized to that agent. The letter is attached in the supplemental study documents.

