For calculation of power for the co-primary endpoint of LDL-C, we anticipate median baseline presentation LDL-C of 110~(90-130)~mg/dL in our patient population. This number is informed by prior ACS trials as well as local experience with the STEMI population treated at the Johns Hopkins Hospital (with approximately 25%-35% of the population already on baseline statin therapy). We expect this LDL-C value to be reduced by approximately 50% by high intensity statin therapy in the standard treatment arm (i.e. to an LDL-C of 55 (40-70) mg/dL at 30 days). We anticipate a further 50% lowering of LDL-C at 30 days after the administration of evolocumab (i.e. to an LDL-C of 28 (14 – 42) mg/dL. As is shown below (Table 1), using a one-sided p-value of 0.05, the study has nearly 100% power to detect this difference, and will have 80% power to detect an absolute LDL-C reduction of only 13.5 mg/dL (24% reduction in LDL-C at 30 days). Additionally, Table 2 presents the expected mean \pm SD baseline and 30-day LDL-C levels and the expected percent changes in the mean LDL-C in the placebo and evolocumab arms.

Table 1:

		Anticipated	Estimated	Detectable
N in each group	Median (IQR)	Percent	Power to	Point
	LDL-C in ACS	LDL-C	Detect a	Estimate at
	Population at	Reduction in	50%	>80%
	baseline	the	Additional	Power
		Standard of	LDL	
		Care Arm	Lowering	
N = 50	110 (90-130)	50% (40 –	99+%	-13.5 mg/dL
		60%)		

Table 2: Expected mean \pm SD LDL-C levels at baseline and thirty-days and the percent change from baseline to 30 days in the placebo and evolocumab groups.

Groups:		LDL-C, mg/dl		% change from	
		Baseline, mean (SD)	30 day, mean (SD)	baseline, mean (SD)	
High	+Placebo	110 (±14)	55 (±11)	-50 (±12)	
dose statin	+Evolocum ab		28 (±10)	-75 (±14)	

For the co-primary FDG-PET assessed myocardial inflammation endpoint, appropriate data necessary for power calculations are currently unavailable. With 50 patients in each arm, applying the overall mean (SD) of 35.4 (18.1) from Ripschler et al [38] as a baseline estimate, we will have 80% power to detect a 30 % difference in FDG-PET assessed myocardial inflammation between the evolocumab and placebo groups.

Secondary Endpoint:

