Previously published clinically relevant, drug-induced TBR changes are reported in the range of 5%-15%. [44] The power calculations for a 10% and 15% TBR difference based on a sample size of 50 patients per study arm are outlined in Table 3 below. Table 1 uses a 1-sided p-value of 0.05, under the hypothesis that evolocumab will lower inflammation and will not raise it,

consistent with the approach used in the Dal-PLAQUE study. Calculations are performed using non-parametric statistics accounting for the possibility of non-normally distributed TBR data.

Tables 3: Power calculations using a 1-sided p-value, i.e. only assumes that PCSK9 inhibition will lower TBR in the most diseased segment (MDS) and will not raise TBR.

Table 3			Estimated	Detectable
	N in each group	Median (IQR)	Power at	Point
		TBR in STEMI	10% & 15%	Estimate at
		Population at 30	TBR	70% &
		days	Difference	80% Power
Aorta	N = 50	3.2(2.7-4.0)	88%	-8.1%
MDS			99%	-9.1%
Carotid	N = 50	2.5 (2.1 – 3.0)	97%	-6.4%
MDS			99%	-7.2%

The table above shows good to excellent power to demonstrate a difference of 10%, and an excellent power to show a difference of 15% in the primary outcome.

Mean and standard deviations of anticipated TBR in STEMI population at 30-days:

 \triangleright Aorta MDS: 3.3 ± 0.6

 \triangleright Carotid artery MDS: 2.6 ± 0.4

Since the timepoint of study drug administration may vary between participants hospitalized at JHH and Bayview, we will create a co-variable to document the time period between hospitalization and study drug administration and adjust our analysis accordingly.

Sample Size Considerations (for the observation study group)

Analysis of Lp(a) in 37 patients in the placebo group of the intervention study indicates an increase in Lp(a) (median, IQR) from 64 [41,187] to 82 [37,265] nmol/L from that obtained during the hospitalization and at 30 days. We would like to obtain an earlier value and correlate the findings with other inflammatory markers and mediators. Given the findings in the above analysis, we believe results in 100 additional patients would provide an adequate sample size.

a. Early stopping rules.

The DSMB will perform any interim analysis they require to monitor patient safety and provide reports advising continuation of the study.

10. Study Statistics (observation study):

Statistical Approach

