Evolocumab in Patients With Acute MI NCT04082442 7/14/2021

Evolocumab in Patients with Acute Myocardial Infarction (NCT04082442)

Study Statistics

Cover Sheet

Title: Evolocumab in Patients with Acute Myocardial Infarction: A Double-blind, Prospective, Randomized, Placebo-Controlled Study

Study Type: Interventional (Randomized, Double-Blind, Placebo-Controlled)

Population: Patients with acute myocardial infarction receiving high-intensity statin therapy

Sample Size: 100 participants (50 per arm: Evolocumab vs. Placebo)

Primary Outcome: Percent change in LDL-cholesterol (LDL-C) from baseline to 30 days

Key Secondary Outcome: Change in myocardial inflammation measured by FDG-PET (mean Standardized Uptake Value, SUV) from baseline to 30 days

Analysis Population: All randomized participants with evaluable baseline and follow-up data

Primary Endpoint Analysis

Endpoint Definition: Difference in the mean percent change in LDL-C from baseline (prerandomization) to 30 days in the evolocumab and placebo groups.

Statistical Method:

- Mean ± SD LDL-C at baseline and 30 days will be summarized for each group.
- Between-group comparisons will use an independent-samples t-test (two-sample test of means).
- Percent change will be calculated as: ((LDL-C30d LDL-Cbaseline) / LDL-Cbaseline) × 100.
- Two-sided p < 0.05 will indicate statistical significance.
- Results will also be presented as mean differences with 95% confidence intervals.

Power Considerations: Assuming baseline LDL-C \approx 110 mg/dL, 50% reduction with standard statin therapy, and an additional 50% reduction with evolocumab, a sample size of 50 per group provides >99% power (one-sided α = 0.05) to detect a 13.5 mg/dL absolute LDL-C difference.

Secondary Endpoint Analysis

Endpoint Definition: Change in inflammation quantified as mean FDG-PET Standardized Uptake Value (SUV) from baseline (index hospitalization) to 30 days in the evolocumab and placebo groups.

Statistical Method:

- For within-group change: paired t-test or Wilcoxon signed-rank test (if non-normal).
- For between-group comparisons: independent-samples t-test or Mann-Whitney U test.
- Data will be presented as mean ± SD and mean difference (95% CI).
- Significance defined as two-sided p < 0.05.

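### The supplementary PET analyses by first-scan timing (within 48 hours of the dose or not) have no planned comparison of the two drug effects, so differing p-values could be misread as a timing effect.

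*Protocol*

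**What the plan says.** Protocol section 2.2 b.i lists the change in FDG-PET myocardial and vascular inflammation between hospitalization and day 30. The section then adds: "separate analyses will also be performed in those who did and did not undergo the initial PET scan within 48 hours of study drug administration". The word 'also' keeps the comparison of all patients.

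The SAP (Secondary Endpoint Analysis) does not mention the 48-hour split. Its between-arm method is one line, "For between-group comparisons: independent-samples t-test or Mann-Whitney U test", followed by presentation of mean differences with 95% confidence intervals and the rule "Significance defined as two-sided p < 0.05". Neither the SAP nor the protocol's section 9 contains an arm-by-timing term, power for the two parts, or a rule for reading the two results together.

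Section 9 of the protocol does define a timing covariate, but it measures the interval from hospitalization to study drug. The 48-hour split concerns the interval from study drug to first scan.

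Section 4.a (Study design) makes clear that late first scans are expected. An outpatient first scan is planned for "those discharged home from Bayview, or Hopkins patients who could not undergo the scan during their admission because of scheduling issues".

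**The concern.** A natural reason to split by first-scan timing is to learn whether a first scan taken well after the dose, and so no longer a clean baseline, changes the measured drug effect. That is a question about the difference between two effects. Each separate analysis instead tests whether there is any effect within its own part. With the sample divided, one part can reach p < 0.05 and the other miss it by chance alone, although the true effect is the same in both.

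What is at stake is how the SAP's key secondary outcome is read. Without a stated rule, a significant result in one part and a non-significant one in the other invites the conclusion that evolocumab's effect shows only with early, or only with late, first scans. The primary LDL-C analysis is not touched.

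**Working it through.** **Inputs**
- Sample size: "Sample Size: 100 participants (50 per arm: Evolocumab vs. Placebo" (SAP cover sheet).
- Myocardial PET mean and SD: "applying the overall mean (SD) of 35.4 (18.1" (protocol section 9). Planned effect: 30% × 35.4 = 10.62 units.
- Two-sided alpha of 0.05 (SAP).
- Share of patients with a first scan within 48 hours: not given. Assumed 50% to 80%, equal in both arms.

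**Step 1. The plan's own figure.** Protocol section 9 says "we will have 80% power to detect a 30 % difference in FDG-PET assessed myocardial inflammation between the evolocumab and placebo groups". Standardised effect = 10.62 / 18.1 = 0.587. A two-sided t-test with 50 per arm has 83% power, consistent with the stated 80%.

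**Step 2. The two parts, with the same true effect in each.** With power p1 and p2 in the two independent parts:

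P(exactly one significant) = p1(1 − p2) + p2(1 − p1)

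| Early / late per arm | Power early | Power late | Exactly one significant | Both | Neither |
|---|---|---|---|---|---|
| 25 / 25 | 53% | 53% | 50% | 28% | 22% |
| 30 / 20 | 61% | 44% | 51% | 27% | 22% |
| 35 / 15 | 68% | 34% | 56% | 23% | 21% |
| 40 / 10 | 74% | 24% | 62% | 18% | 20% |

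For 25 / 25: 2 × 0.529 × 0.471 = 0.498. Simulation of 20,000 trials per setting agreed for 25 / 25 and 35 / 15. In the same simulations a test of arm-by-timing interaction wrongly declared a difference in about 5% of trials.

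**Step 3. Away from the planned effect, at an equal split.**
- No effect: 2 × 0.05 × 0.95 = 9.5%.
- Half the effect (15%): power 17.4% in each part, so 2 × 0.174 × 0.826 = 29%.
- 1.5 times the effect (45%): power 86.2% in each part, so 2 × 0.862 × 0.138 = 24%.

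At an equal split, 50% is the highest value that 2p(1 − p) can take.

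**Step 4. Vascular PET.** Section 9 gives "Aorta MDS: 3.3 ± 0.6" and a carotid value of 2.6 with SD 0.4. For a 10% difference (0.33 and 0.26), two-sided 0.05 and the same range of splits, exactly one part is significant in 50% to 60% of trials (aorta) and 47% to 64% (carotid).

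**Step 5. Sensitivity to the SD.** 18.1 is the SD of single-time values, while the endpoint is a change. With equal SDs at both scans, SD of change = 18.1 × √(2(1 − r)). The correlation r is not given; assume 0.3 to 0.7.
- r = 0.3: SD 21.4, power 40% in each part at 25 / 25, exactly one significant 48%.
- r = 0.5: SD 18.1, as in Step 2.
- r = 0.7: SD 14.0, power 75%, exactly one significant 38%.

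**Step 6. What an interaction could show.** At an equal split, SE = 18.1 × √(2/25 + 2/25) = 18.1 × 0.4 = 7.24. The difference between parts detectable with 80% power is (1.960 + 0.842) × 7.24 = 20.3 units, or 57% of 35.4. For a difference of 10.62, 10.62 / 7.24 = 1.47, which gives about 31% power.

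**The case against.** The timing analyses are supplementary. The all-patient comparison stays, and it is the only between-arm PET analysis in the SAP. A reader might infer that the PET outcome is replaced by two subgroup results; the documents do not support that.

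Nor does either document say that the two results will be compared, or that an effect will be claimed in one timing group only. The split may be meant as a sensitivity analysis asking whether the result holds where the first scan is close to a true baseline. For that purpose the estimate within that part is what is wanted. The SAP's PET methods also call for mean differences with 95% confidence intervals, and from two independent estimates with intervals a reader can work out the difference and its uncertainty.

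A reader might also infer an inflated error rate. With no drug effect, at least one of three tests (all, early, late) is significant in 11% to 12% of simulated trials. That counts two supplementary analyses as confirmatory tests, a status the documents do not give them.

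One might call a split verdict the most likely outcome. At 25 / 25 that holds only if early-only (25%) and late-only (25%) are merged; both parts significant has 28%.

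Finally, the interaction is weak at this sample size. These points limit the size and seriousness of the matter. What stands is that the plan has a significance threshold and no rule for reading the two parts against each other. Low power for the interaction is no argument for two separate p-values, which draw on the same data.

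**Conclusion.** The point holds as a gap in a supplementary analysis of the key secondary outcome. At the planned 30% myocardial effect, with an identical true effect in both parts and an assumed early-scan share of 50% to 80%, exactly one part would reach significance in about 50% to 62% of trials. This is not a general rate: at an equal split it is about 10% with no effect, 29% at half the effect and 24% at 1.5 times. It rests on an early-scan share that the documents do not give, on balance of timing between arms, and on a single-time SD used for a change endpoint, so it is approximate.

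The hospitalization-to-drug covariate does not close the gap, because it is a different interval and an adjustment rather than a comparison of effects. The documents do not support a claim that the main PET comparison is invalid or that the investigators intend a subgroup claim.

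**What to change.** In protocol section 2.2 b.i and in the SAP's Secondary Endpoint Analysis:

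1. State that the all-patient comparison is the only test of the drug effect on PET, and label the 48-hour analysis supportive and exploratory.
2. Replace the two separate tests with one model on all evaluable patients: arm, first-scan timing (within 48 hours of the dose, yes or no), arm × timing, and site as a covariate.
3. Report the arm effect at each timing and the interaction estimate, each with a 95% confidence interval, with no significance claim within a timing group.
4. Base any statement that the effect depends on scan timing on the interaction only.

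The cost is wording and analysis code; no new patients or data are needed. There are three limits to state in the SAP. The interaction is imprecise (about 31% power for a difference of 10.62 units and 80% only for about 20.3 units, at an equal split). A non-significant interaction does not show that timing is irrelevant. Late first scans are partly tied to site, though Hopkins patients with scheduling problems contribute too, so a site main effect does not fully separate timing from site.
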